APPENDIX B: STEPS FOR MULTIPLE IMPUTATION

For the MI to be applied to the MMRM for the sensitivity analysis of the primary efficacy endpoint, the following steps will be followed:

Imputation distribution

The imputation distribution for the missing absolute change from baseline at visit t (eg. Week 4, Week 8) will be a normal distribution.

Imputation algorithm

We will use the following algorithm that relates the mean of the missing absolute change from baseline at visit t. The algorithm will be implemented within each treatment group separately by each visit as follows:

randomly draw a sample from the normal distribution (μ, σ^2) , where μ is the mean of the non-missing absolute changes from baseline at visit t and σ^2 is the sample variance estimated using the non-missing absolute changes at visit t.

Analysis model

The complete MI method is described below:

- Form an "imputed dataset" by imputing missing change from baseline values at • each visit for those subjects who have a missing value at the visit. The appropriate normal distribution specified in the algorithm above will be used for each such subject.
- Repeat this process K (K=20) times to form K imputed datasets.

BlackThorn Therapeutics, Inc.	Statistical Analysis Plan
K2-MDD-201	Version 2.0; 03 June 2022

- Fit the same MMRM model as the one used for primary analysis to each imputed dataset to estimate the absolute change.
- Combine the results from the analyses of K imputed datasets using the SAS procedure MIANALYZE to derive the MI estimator.

Let θ be the true treatment difference. Denote by $\tilde{\theta}_k$ the estimate of θ from the k^{th} imputed dataset, and the corresponding estimate of the variance is denoted by V_k . The MI estimator of θ , $\tilde{\theta}_{\text{MI}}$, is the average of the K individual estimates.

The estimated variance of $\tilde{\theta}_{MI}$ is a combination of the between- and within-imputation variability as follows: $V_{MI} = W + \left(1 + \frac{1}{K}\right)B$, where $W = \frac{1}{K}\sum_{k=1}^{K}V_k$ is the within-imputation variability and is $B = \frac{1}{K-1}\sum_{k=1}^{K}(\tilde{\theta}_k - \tilde{\theta}_{MI})^2$ is the between-imputation variance. The statistic $T = \frac{\tilde{\theta}_{MI} - \theta}{\sqrt{V_{MI}}}$ has an approximate t_V distribution Rubin (1987), where $V = (K-1)(1 + \frac{W}{R})^2$.

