7.1.2 Analysis Visit Window

For efficacy analyses and safety analysis by visit, assessments at scheduled and unscheduled visits will be mapped to the appropriate analysis window as detailed in Table 3 and Table 4. In the event where more than one visit falls in the same analysis window, the following rules will be used in sequence to determine the record that will be analyzed:

- If there is a scheduled visit in the analysis window, then the scheduled visit's data will be used.
- If there is no scheduled visit in the analysis visit window, the data closest to the scheduled day/time visit will be used.
- If there is no scheduled visit in the analysis visit window and there is a tie between the visits with regards to the number of days/hours before and after the scheduled day, the later data will be used.

Visit windows will not apply to listings. All data will be included in subject listings.

Windowing will be applied to the data prior to any missing data calculations.

Confidential

Period	Screening	Baseline	Study Drug Treatment Safety Follow-up					ollow-up
Visit	1	2	3	4	5	6		
	Days –7 to –28	Day 1	Day 15 (±2 d)	Day 29 (±2 d)	Day 43 (±2 d)	Day 57 (±2 d)	Day 71	Day 85
Analysis Visit Name		Baseline *	Week 2	Week 4	Week 6	Week 8	Week 10	Week 12
CGI-I HADS	NA	≤1 Pre- dose	[2, 22]	[23, 36]	[37, 50]	[51, 71]	NA	NA
HAMD-17 HAM-A SHAPS		≤ 1 Pre-						
	NA	dose	NA	[16, 43]	NA	[44, 71]	NA	NA
CGI-S	NA	≤1 Pre- dose	NA	NA	NA	[44, 71]	NA	NA
SDS	NA	≤1 Pre- dose	NA	[23, 36]	[37, 50]	[51, 71]	NA	NA

Table 3Analysis Windows for Efficacy Analyses

* Baseline for analysis visit refers to baseline value for efficacy analysis defined in Section 7.1.5

Period	Screening	Baseline	s	Study Drug Treatment				ollow-
Visit	1	2	3	4	5	6		
	Days -7 to -28	Day 1	Day 15 (±2 d)	Day 29 (±2 d)	Day 43 (±2 d)	Day 57 (±2 d)	Day 71	Day 85
Analysis Visit Name		Baseline	Week 2	Week 4	Week 6	Week 8	Week 10	Week 12
Vital signs Clinical laboratory tests COWS	NA	≤1 Pre- dose	[2, 22]	[23, 36]	[37, 50]	[51, last dose +30]	NA	NA
Body weight ECG	NA	≤1 Pre- dose	NA	[2, 43]	NA	[44, last dose +30]	NA	NA
Standard Ophthalmologic examination	NA	≤1 Pre- dose	NA	[2, 14]	NA	≥ 15	NA	NA
Corneal specular microscopy	NA	≤1 Pre- dose	NA	NA	NA	NA	NA	≥2
C-SSRS	Nominal	≤ 1 Pre- dose	[2, 22]	[23, 36]	[37, 50]	[51, 64]	[65, last dose +30]	NA

Table 4Analysis Windows for Safety Analyses by Visit

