7.2 Analysis Populations

The analysis populations are defined as follows:

- The Safety population is defined as all subjects who received study drug and will be used for summaries of safety parameters. Subjects will be analyzed according to treatment received.
- The Efficacy population includes all randomized subjects who received at least 1 dose of study drug, have a baseline HAMD-17 assessment total score, and have at least 1 post-baseline HAMD-17 assessment total score. Subjects will be analyzed according to randomized treatment assignment. This population will be used for the primary analysis and for all other efficacy analyses.
- The Per-Protocol (PP) population includes subjects in the efficacy population except those who experienced an important protocol deviation that is determined to substantially impact efficacy analysis, or did not have a HAMD-17 score at Week 8 analysis visit, or whose compliance at the end of the study was less than 70%. Subjects will be analyzed according to randomized treatment assignment. This population will be used for supportive efficacy analyses. The list of important protocol deviations for PP population will be classified by the sponsor before the final database lock and the unblinding of the study.

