7.4.4 Primary Efficacy Endpoint Analysis Methods

The primary efficacy endpoint is the change from baseline to Week 8 on the HAMD-17 score. The estimand for the primary efficacy endpoint is the difference in means between treatment groups in the change of HAMD-17 scores from baseline to Week 8 for all subjects in the Efficacy population. For efficacy analyses, baseline is defined as the latest measurement prior to the first administration of study drug. The null hypothesis to be tested is that there is no difference between BTRX-335140 and placebo:

H₀:
$$\mu_A = \mu_{B_i}$$

Where μ_A and μ_B represent the mean values for BTRX-335140 and placebo, respectively. The alternate hypothesis to be tested is that the treatment group means differ:

H₁:
$$\mu_A \neq \mu_{B}$$
;

The analysis will be conducted using a mixed-models repeated measures (MMRM) with change from baseline in HAMD-17 score as the dependent variable and will include treatment group, week, and week by treatment group interaction as factors, and baseline HAMD-17 score as covariate. Variance estimation will be based on an unstructured covariance matrix. If the unstructured covariance matrix results in a lack of convergence, the heterogeneous autoregressive variance-covariance structure will be used.

The primary analysis will compare the groups at Week 8. The primary results obtained from the model will be the estimated treatment difference at Week 8. Significance will be assessed based on a two-sided test at the α =0.05 level of significance. In addition, the estimated treatment difference at Week 4 will be provided. The model-based least square (LS) means, standard errors, 95% CIs, and 2-sided p-values will be reported.

In addition, descriptive summary of HAMD-17 and each individual item will be generated by treatment group and by visit.

BlackThorn Therapeutics, Inc.	Statistical Analysis Plan
K2-MDD-201	Version 2.0; 03 June 2022

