7.4.5 Sensitivity Analyses of the Primary Efficacy Endpoint

Sensitivity analyses will be used to investigate the impact of important protocol deviations or missing data for the primary efficacy endpoint assessment (ie, HAMD-17 total score). The primary efficacy analysis will be repeated using

- The per-protocol population.
- If ≥10% of subjects have missing data for the primary efficacy endpoint assessment (i.e., HAMD-17 total score), the following will be conducted:
 - Rubin's rules for multiple imputation (MI) with SAS Proc MI and MIANALYSIS for the efficacy population. See Appendix B : Steps for Multiple Imputation for further details.
 - Last Observation Carried Forward (LOCF) Imputation technique, ie, the last observed non-missing value will be used to fill in missing values at a later point in the study, regardless of when the missing value occurred. The imputed dataset generated with the LOCF technique will be used as input data in the ANCOVA. The efficacy population will be used.

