- ^a Study site personnel will contact subjects by telephone for Safety Follow-up assessments (adverse events, concomitant medication usage, and C-SSRS) approximately 2 weeks after discontinuation of study drug.
- ^b Visit 1 procedures may be completed over 2 days, if necessary.
- ^c Subjects who discontinue early will complete an EOT visit <2 days after their last dose of study drug; efficacy assessments are to be performed only if the subject has remained on study drug. For subjects who do not return, the site should complete a C-SSRS if they are aware of a potential suicide-related thought or behavior by other communications. The 12-week corneal specular microscopy examination should still be conducted approximately 12 weeks after the first dose of study drug (Section 7.7.2 of the protocol).

- ^d Inclusion/exclusion criteria must be reconfirmed for eligibility prior to randomization.
- ^e Collect vital signs measurements (respiratory rate first, then blood pressure and pulse) after subject has been supine for 10 minutes; subjects should then stand for 3 minutes before obtaining standing vital signs measurements [see Section 6.3.4 of the protocol]. Oral temperature can be assessed in any position.
- ^f A full physical examination involving an evaluation of cardiovascular, respiratory, gastrointestinal, neurological (examination of cranial nerves, motor system, sensory, and reflexes), dermatological, and musculoskeletal systems, and include general appearance, skin, head, neck, eyes, ears, nose, throat, lungs, heart, abdomen, back, lymph nodes, extremities, and vascular status will be conducted at the screening visit. Further physical examination will be conducted as needed. (Section 6.3.3 of the protocol).
- ^g At Screening, collect height for BMI calculation.
- ^h Ophthalmologic examinations will be performed by a site-affiliated ophthalmologist. Details for the standard ophthalmologic examination and corneal specular microscopy will be described in a separate ocular monitoring manual. Additional standard ophthalmologic exams and / or corneal specular microscopies may be conducted to assess subject safety.
- ⁱ Baseline ophthalmologic examinations (standard and corneal specular microscopy) must be performed before randomization.
- ^j Prior to Visit 3 (Week 2) (between Days 7 and 14 [+2 days]), a standard ophthalmologic examination will be performed.

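### The multiple-imputation check in SAP Appendix B ignores baseline and Week 4 scores, so it acts as an observed-case analysis and assumes more about missing data than the MMRM it is meant to probe

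*SAP*

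**What the plan says.** SAP 7.4.5 lists the sensitivity analyses for the primary endpoint. Their stated purpose is to look at the effect of protocol deviations and missing data. Two of them run only if at least 10% "of subjects have missing data for the primary efficacy endpoint assessment (i.e., HAMD-17 total score), the following will be conducted": multiple imputation, described as "rules for multiple imputation (MI) with SAS Proc MI and MIANALYSIS for the efficacy population", and LOCF followed by ANCOVA. For the imputation method the reader is sent to Appendix B.

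Appendix B draws each missing change from a normal distribution. The mean "is the mean of the non-missing absolute changes from baseline at visit t and" the variance is the sample variance of the same observed changes. On scope it says: "The algorithm will be implemented within each treatment group separately by each visit as follows". Twenty datasets are filled in, the primary MMRM is fitted to each, and the results are combined with MIANALYZE. No baseline term, no other-visit term and no draw of the parameters appears.

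The primary model (SAP 7.4.4) has treatment, week, their interaction and baseline HAMD-17. It also states: "Variance estimation will be based on an unstructured covariance matrix". SAP Addendum 5.2.2 revises LOCF only, so Appendix B stands as written.

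Three other places show what data exist for subjects without a Week 8 score:
- Efficacy population, SAP 7.2: subjects must "have at least 1 post-baseline HAMD-17 assessment total score".
- SAP 7.1.2: scheduled and "unscheduled visits will be mapped to the appropriate analysis window". In Table 3, HAMD-17 has only two post-baseline windows, Week 4 (Days 16 to 43) and Week 8 (Days 44 to 71).
- SAP Appendix A, footnote c: "Subjects who discontinue early will complete an EOT visit". An on-drug score taken at that visit on Days 16 to 43 falls in the Week 4 window.

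**The concern.** A subject without a Week 8 score usually has a Week 4 score. The MMRM uses it through the unstructured covariance. Appendix B discards it, and refitting the MMRM to the filled-in data cannot bring it back, because the imputed Week 8 values carry no Week 4 information. The imputed values are centred on the mean of those who stayed, so the result follows the observed-case comparison.

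The MMRM is valid if missingness depends only on the data it uses (MAR). Appendix B is valid only if, within each arm, missingness does not depend on the scores at all. A check that can be biased where the primary analysis is sound does not show whether the primary analysis is robust. The error can go either way: a sound result may look fragile, or a fragile one may look robust.

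**Working it through.** **Inputs.** From the documents: about 180 subjects randomised 1:1, so 90 per arm; K = 20; the Appendix B algorithm; the SAP 7.4.4 model. Assumed, because the documents show no value: Week 8 SD 7 (range 6 to 8), Week 4 to Week 8 correlation ρ = 0.65 (range 0.5 to 0.75), and dropout. Missing means no score in the Week 8 window. The dropout model is logit P(missing) = a + β·z4, where z4 is the Week 4 change standardised within arm and a is set to give the chosen missing fraction p.

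**Formula.** The expected Week 8 change among those observed in an arm is that arm's true mean plus ρ × SD × E(z4 | observed). Appendix B centres the imputed values there too, so

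bias = ρ × SD × |difference between arms in E(z4 | observed)|.

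The size of E(z4 | observed), by numerical integration:

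| Missing p | β = 0.5 | β = 1 |
|---|---|---|
| 10% | 0.0488 | 0.0908 |
| 20% | 0.0962 | 0.1732 |
| 30% | – | 0.2528 |

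**Results**, with ρ × SD = 0.65 × 7 = 4.55:
- β of 1 in one arm and 0.5 in the other, 10% missing: 4.55 × (0.0908 − 0.0488) = 0.19. At 20%: 4.55 × (0.1732 − 0.0962) = 0.35. With ρ × SD from 0.5 × 6 = 3.0 to 0.75 × 8 = 6.0, the ranges are 0.13 to 0.25 and 0.23 to 0.46.
- Only one arm depends on Week 4 (β = 1), an extreme case: 4.55 × 0.0908 = 0.41 at 10% and 4.55 × 0.1732 = 0.79 at 20%.
- Same β = 1 in both arms, unequal rates: 10% against 20% gives 4.55 × (0.1732 − 0.0908) = 0.375, given here as 0.38. 10% against 30% gives 4.55 × (0.2528 − 0.0908) = 0.74.
- Same β and same rate, or random missingness: zero.

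**Scale.** At 10% missing about 81 per arm are observed, so SE ≈ 7 × √(2/81) = 1.10 and 0.19 is 0.17 SE. At 20%, SE ≈ 7 × √(2/72) = 1.17 and 0.35 is 0.30 SE.

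**Simulation** (4,000 trials per scenario, K = 20). With β of 1 and 0.5 and no true effect, the bias was +0.20 with placebo the stronger arm and −0.17 with drug the stronger at 10%, and +0.34 and −0.34 at 20%. Rejection was 5.1% to 6.2% at 10% and 5.9% to 6.9% at 20%, against 4.3% to 5.7% for the MMRM over all scenarios. With equal β and equal rates the bias was 0.02 or less. Appendix B correlated 0.991 to 0.996 with complete-case ANCOVA. If a quarter of those missing have no score in either window, the 1 against 0.5 bias falls to about 0.15 and 0.30.

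With a true difference of −2.5 and the same unequal dependence at 20% missing, Appendix B averaged −2.15 with one arm the stronger and −2.84 with the other. The chance of p < 0.05 was 48% or 70%, against 61% for the MMRM.

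**Independent simulation** (300 trials per scenario, true difference −3, slightly different SDs). One-arm dependence gave +0.41 at 10%, and +0.69 (placebo) or −0.77 (drug) at 20%. The same β = 1 with 30% missing on placebo and 10% on drug gave +0.76. The same rule and rate gave −0.04. The MMRM stayed within 0.07. Imputing within arm from baseline and Week 4 gave −0.07 to +0.03. This run did not cover the 1 against 0.5 case or the rejection rates.

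**The case against.** The strongest reply is that little rests on this analysis. It is a conditional sensitivity check with no decision rule. A reader might infer that the primary result is biased or that type I error is inflated for the trial's conclusion. The documents do not support that: the primary test is the MMRM, and Appendix B does not touch it.

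LOCF runs under the same trigger and, as revised by the addendum, carries each leaver's last post-baseline score to Week 8. It would be wrong to say that no sensitivity analysis uses the Week 4 scores, and a gap between MI and LOCF would be visible. This stands, but LOCF has its own bias and does not repair Appendix B.

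Unequal dropout is assumed. Protocol 4.4 and 5.4 allow leaving for unsatisfactory effect and for intolerance, which makes it plausible. A reader might go further and expect more intolerance dropout on drug. The only tolerability data shown (Protocol 1.1.3: short dosing in healthy subjects) report no discontinuations due to adverse events and findings comparable with placebo. They neither support that expectation nor settle the matter for 8 weeks in patients. SAP 7.3.1 tabulates reasons for leaving by arm, which helps interpretation but does not correct the estimate.

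The MMRM's own validity is also conditional. Under SAP 7.1.2 a scheduled Week 4 score takes precedence, so a later early-termination score in the same window may go unused, and worsening after Week 4 could bias the MMRM too. This stands.

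Two details are minor. The missing parameter draw alone makes the SE only about 0.5% (at 10% missing) to 2% (at 20%) too small. The procedure name in 7.4.5 is a slip, since Appendix B has MIANALYZE.

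**Conclusion.** The concern holds. As written, the Appendix B check is close to an observed-case analysis and assumes missingness completely at random within arm, which is stricter than the MAR assumption of the MMRM. A gap between the two results would not be evidence against the MMRM.

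The size is modest in the central case: under 0.2 SE at 10% missing. It grows with the missing fraction and with any imbalance. It is not safe to infer that a shared dropout mechanism removes the problem: the missing rates must be equal too. All sizes scale with ρ × SD and rest on assumed SD, correlation and dropout. The number of subjects whose only post-baseline score falls outside both windows, for example before Day 16, is not given. The reading of Appendix B itself rests on no assumption.

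This should be corrected, but it does not threaten the primary analysis.

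**What to change.** Rewrite Appendix B. Within each arm, use PROC MI to impute the Week 4 and Week 8 changes from baseline HAMD-17 and the other visit, with parameters drawn from their posterior (MCMC first for intermittent gaps, then regression). Subjects with no score in either window are imputed from baseline at Week 4, then at Week 8. Fit the primary MMRM to each dataset and combine with PROC MIANALYZE. Align SAP 7.4.5 to name this one method. LOCF can stay.

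This version will largely reproduce the MMRM: in simulation the means agreed within 0.005. An optional but recommended addition is therefore a step that departs from MAR in a controlled way. One form adds a delta to imputed Week 8 changes in the BTRX-335140 arm, in 1-point steps. Each step moves the estimate by the drug-arm missing fraction, 0.1 at 10% and 0.2 at 20%. The other form is reference-based imputation from placebo. Either is a new analysis, not a correction of Appendix B.

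Cost: a rewritten appendix, one line in 7.4.5, a few lines of SAS and some extra runs. No new data are needed and the primary analysis does not change. The sensitivity results may turn out less favourable.
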